## 10.1.1 Adverse Events Leading to Discontinuation of Study Drug

A listing of AEs leading to discontinuation of study drug will be provided, displaying details of the event(s) captured on the CRF.

#### 10.1.2 Serious Adverse Events

A listing of SAEs will be provided, displaying details of the event(s) captured on the CRF.

#### **10.1.3** Deaths

A listing of deaths will be provided for the Safety Population.

#### 10.2 Clinical Laboratory Evaluations

Laboratory tests will be performed at the Screening and End of Study (or early discontinuation) visits and include analytes for Serum Chemistry and Hematology. Pregnancy tests will be performed on all women of child-bearing potential at screening and every month [+ or -7 days] after randomization to ensure no pregnancy prior to study drug administration. The urine drug abuse screen will be performed at screening and will test for amphetamines, barbiturates, cocaine, phencyclidine (PCP), and meth/amphetamines.

Laboratory values will be displayed in the by-subject data listings for the Safety Population and those that are outside the normal range ("H" or "L") will be flagged,

Protocol: CP-2019-001 Page 22 of 26

Final Version 1.0

along with corresponding normal ranges. Pregnancy data collected throughout the study will be listed, as well as results from the urine drug abuse screen.

## 10.3 Vital Signs

All subjects will have vital signs (temperature, RR, BP, and HR) measured at the Screening, Randomization (Day 1), and End of Study (or early discontinuation) visits.

A by-subject listing of all vital sign data will be provided.

## 10.4 Physical Examination

A physical examination including height and weight will be performed during the Screening, Randomization (Day 1), and End of Study (or early discontinuation) visits. Height will be collected at screening only. The physical examination will include, but is not limited to, HEENT, dermatologic (investigator skin assessment), brief neurological, general appearance, lymph nodes, cardiovascular, respiratory, gastrointestinal, and musculoskeletal examination.

Abnormal PE findings will be listed by subject; clinical significance will be indicated as well as the abnormality specified. In addition, a by-subject listing height and weight data will be generated.

## 10.5 Electrocardiogram (ECG)

A 12-lead ECG will be performed at the Screening and End of Study (or early discontinuation) visits. The standard ECG parameters including rhythm, heart rate, and intervals for PR, QRS, QT, QTcB and QTcF (Fridericia's) correction for heart rate will be recorded. A listing of abnormal ECGs will be generated along with clinical significance as determined by the Investigator, any Investigator comments, and the results for all ECG parameters. A by-subject data listing of all ECG results will also be provided for each visit.

## 10.6 Investigator Visual Skin Assessment

The Investigator will perform a visual skin assessment of bruising, erythema, and edema at the randomization visit (Visit 2) and at the End of Study (or early discontinuation) visit. Any adverse events including application site reactions will be documented on the appropriate eCRF page and must be followed until resolution or medically stable.

At the End of Study (or early discontinuation) visit, the entire surface area of the outer upper arm where the two patches were applied will be assessed for the following skin signs or symptoms. Any findings with an intensity rating of 1 (Mild intensity), 2 (Moderate intensity), or 3 (Severe intensity) must be recorded as an adverse event in the eCRF and followed to resolution.

Protocol: CP-2019-001 Page 23 of 26 Final Version 1.0

Bruising assessments (visual rating) will be performed using the following ratings:

Symptom	Intensity Rating (circle)
Bruising where	0 = Clear
C213 was applied?	1 = Mild intensity
T.F.	2 = Moderate intensity
	3 = Severe intensity

The following ratings will be used to describe the amount of erythema and edema indicative of irritation:

Symptom	Rating (circle)
Skin Erythema	0 = Clear
where C213 was applied?	1 = Mild intensity
Tr. F	2 = Moderate intensity
	3 = Severe intensity

Symptom	Rating (circle)
Skin Edema	0 = Clear
where C213 was applied?	1 = Mild intensity
	2 = Moderate intensity
	3 = Severe intensity

A by-subject data listing for bruising, erythema, and edema will be provided for each subject that has a rating of anything but 'Clear' at any visit and for those subjects who did not have the investigator skin assessment performed.

Protocol: CP-2019-001 Page 24 of 26

Final Version 1.0

#### 11. MEDICATIONS

#### 11.1 Concomitant Medications

All medications will be coded using WHODrug-Global-B3 version March 2019. Prior and concomitant medications will be summarized by treatment group and by the number and percentage of subjects taking each medication, classified by using WHO-DD Anatomical Therapeutic Chemical Level 3 and preferred term.

Prior medications are defined as medications or therapies initiated prior to the start of patch administration. Concomitant medications are defined as any medications other than the study drug that a subject receives concurrently with the study drug. These medications will have start dates on, prior to, or within 5 days after the date of patch administration and end dates on or after the date of patch administration. Any medication that was stopped more than 90 days prior to informed consent will not be considered prior or concomitant.

Prior and Concomitant medications will be summarized. All medications will be presented in a listing.

Please refer to Section 7.3 for the conventions used to impute partial start dates and end dates of concomitant medications.

## 11.2 Extent of Exposure

Treatment duration is defined as 30 minutes (time that the patch should remain on the subject).

Extent of exposure to study medication will be tabulated by treatment group by summarizing the frequency and percentage of subjects whose patch stayed on for 30 minutes as collected in the CRF.

A listing of drug accountability data based on CRF data will be provided.

### 12. CHANGES FROM PLANNED ANALYSIS

Due to insufficient enrollment numbers, the CMH test as described in the protocol for the primary and secondary analyses will not be performed. The protocol also describes a fixed sequential procedure to control for overall type 1 error. This will not be implemented since the actual number of randomized subjects is quite a bit less than planned and the pre-specified statistical analyses as described in the protocol cannot be performed.

Protocol: CP-2019-001 Page 25 of 26

Final Version 1.0

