7.4 Efficacy Analysis

7.4.1 Primary Analysis

The co-primary efficacy endpoints are the proportion of subjects who achieve pain relief at 15 minutes and the proportion who achieve sustained pain relief from 15 minutes to 60 minutes post patch application. These two endpoints will be analyzed separately using a Cochran Mantel Haenszel test stratified by cluster headache subtype (episodic or chronic) and will utilize the mITT population. A significance test of the treatment difference comparing each C213 dose to

placebo will be tested at the two-sided 0.05 level, and odds ratios and their corresponding 95% confidence intervals will be calculated. Headache pain will be assessed using a 4-point scale (0 = none, 1 = mild, 2 = moderate, 3 = severe), with pain relief defined by a decrease in pain from severe to mild or none without the use of acute rescue medication. Sustained pain relief requires a pain rating of mild or none at each timepoint from 15 minutes to 60 minutes without the use of acute rescue medication. Handling of missing data as well as sensitivity analyses will be described in the SAP.

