7.4.2 Secondary Analyses

Secondary endpoints will be analyzed using similar methods as the primary endpoints and will utilize the mITT population.

To adjust for multiplicity and to control for overall type I error, a fixed sequential testing procedure will be applied to the primary analyses for the two C213 arms and the secondary efficacy analyses. If the primary efficacy analyses for the 3.8 mg arm both produce a result that is statistically significant at the 0.05 level, a significance level of 0.05 will be used for the primary analyses of the 1.9 mg arm and for the secondary efficacy analyses in an ordered fashion. If any subsequent analysis does not produce a statistically significant result at the 0.05 level, then the remaining analyses will automatically be considered non-significant. The order of testing for each endpoint and each C213 dose group will be provided in the SAP.

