## 7.1.1 Adjustments for Multiplicity and Other Alpha Control

There will be no adjustments made for multiplicity to control the overall type I error.

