#### 9. EFFICACY ANALYSES

## 9.1 Primary Efficacy Analysis

The proportion of subjects who achieve pain relief at 15 minutes and the proportion who achieve sustained pain relief from 15 minutes to 60 minutes post patch administration will be analyzed separately using Fisher's Exact test, with missing data imputed using LOCF (see section 7.1.3). The analyses will include all subjects in the mITT population. A significance test of the treatment difference comparing each C213 dose (1.9 mg and 2.8 mg) to placebo will be tested at the two-sided 0.05 level.

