#### 9.2 Secondary Efficacy Analyses

Binary data, with the exception of rescue therapy use, will be summarized by treatment group. Missing data will be imputed using LOCF. Summaries of the proportion of subjects will be calculated and displayed, and a Fisher's Exact test will be performed. Two-sided p-values for the test of no difference between each C213 treatment group and placebo will be provided. Rescue therapy use as reported on the eDiary will be listed by subject and timepoint.

Protocol: CP-2019-001 Page 20 of 26

Final Version 1.0

These endpoints will include:

• Proportion of subjects that achieve pain relief at 5, 10, 20, and 30 minutes post patch application

- Proportion of subjects that achieve sustained pain relief from 5 to 60 minutes and from 10 to 60 minutes post patch application
- Proportion of subjects that achieve pain freedom at 10 minutes and 15 minutes post patch application
- Proportion of subjects that achieve sustained pain freedom from 10 to 60 minutes and from 15 to 60 minutes post patch application
- Proportion of subjects using rescue therapy within 20 minutes post patch application
- Proportion of subjects able to perform their usual daily activities as assessed by the subject at 5, 10, 15, 20, 30, and 60 minutes post patch application

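### SAP 12 drops the protocol's fixed test order because of low enrolment, which does not require it, and does not name the loss of the odds ratios with 95% CIs

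*SAP*

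**What the plan says.** **Protocol.** Section 7.4.1 plans a CMH test stratified by headache subtype for each co-primary endpoint and each dose against placebo, and adds that "odds ratios and their corresponding 95% confidence intervals will be calculated". Section 7.4.2 sets a fixed sequence. Both co-primaries must be significant for 3.8 mg before the 1.9 mg co-primaries and the secondaries are tested in order, and testing stops at the first failure. The full order is left to the SAP: "The order of testing for each endpoint and each C213 dose group will be provided in the SAP".

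**SAP.** Section 7.1.1 gives no order: "There will be no adjustments made for multiplicity to control the overall type I error". Section 9.1 replaces CMH by Fisher's exact test, and each dose compared "to placebo will be tested at the two-sided 0.05 level". For the secondaries, section 9.2 says "Two-sided p-values for the test of no difference between each C213 treatment group and placebo will be provided". Neither section mentions an odds ratio or a CI. (Section 9.1 prints the higher dose as 2.8 mg, against 3.8 mg elsewhere. Those passages must be reconciled, but that is a separate matter.)

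Section 12 lists two changes. One is that "the CMH test as described in the protocol for the primary and secondary analyses will not be performed", because of insufficient enrolment. The other concerns the sequence: "This will not be implemented since the actual number of randomized subjects is quite a bit less than planned", with the further reason that the protocol's pre-specified analyses cannot be performed. Odds ratios and CIs are not mentioned there.

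**The concern.** A fixed sequence only sets the order in which p-values are read. Sample size governs its power, not its validity. Small numbers can justify exchanging one test for another, but the new p-values can still be read in the old order. Without an order or a nominal label, a single secondary result with p≤0.05 could be presented as a finding although no rule limits its error rate.

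The second loss matters most in a small trial. A non-significant p-value from few subjects says little unless the uncertainty of the effect is shown. The arm-level proportions remain, so a difference can be read off, but no interval is specified for it. SAP 9.1.1 speaks of treatment estimates that are never defined. Apart from the abbreviation list, 95% CIs appear in the SAP only as an optional summary for continuous variables (13.1.2).

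**Working it through.** **1. The plan's own figure.** Inputs (protocol 7.2, SAP 5): 20% vs 55%, two-sided alpha 0.05, continuity-corrected chi-square, 40 per arm, 15% dropout, so 40 × 0.85 = 34 evaluable.
- Uncorrected: n = [1.96·√(2·0.375·0.625) + 0.842·√(0.16 + 0.2475)]² / 0.35² = 28.8.
- Corrected: (28.8/4)·[1 + √(1 + 4/(28.8·0.35))]² = 34.3, so 35 evaluable per arm.
- Inverting the formula at 34 gives 79.6% power. The stated 80% reproduces.

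**2. Number of tests.** Per dose there are 2 co-primaries and 16 secondaries: relief 4, sustained relief 2, freedom 2, sustained freedom 2, daily activities 6. That is 18 × 2 = 36. Rescue use would add 2, making 38. SAP 9.2 is unclear on this, because it says "Binary data, with the exception of rescue therapy use, will be summarized by treatment group" and then includes rescue use in the endpoint list.

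**3. Are ordered Fisher tests valid at small N?** Exact enumeration of the two-sided Fisher test at p≤0.05, equal arms. The per-arm numbers are assumed, because the documents give no actual N.

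| Evaluable per arm | 6 | 10 | 15 | 20 | 34 |
|---|---|---|---|---|---|
| Largest size over null rates | 0.6% | 1.3% | 1.8% | 2.5% | 3.1% |
| Power, 20% vs 55%, one endpoint | 5% | 19% | 34% | 53% | 82% |

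The first gate needs both 3.8 mg co-primaries, so under the global null its error, and that of the whole sequence, cannot exceed the first row. Low N reduces power only.

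**4. Without the order.** Chance of at least one p≤0.05 under the global null. This was simulated with a shared placebo arm, latent-normal pain scores under several correlation structures, and flat or rising relief over time, at 6,000-10,000 runs per cell. The 20% null rate is the planning value; 35% is the higher 15-minute placebo rate in protocol 1.2.

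| Per arm | 6 | 10 | 15 | 20 |
|---|---|---|---|---|
| 36 tests, 20% rate | 1-3% | 9-12% | 18-26% | 27-35% |
| 36 tests, 35% rate | 5-7% | 14-21% | 25-30% | 33-40% |
| 4 co-primary tests, 20% rate | 0% | 1-2% | 3-5% | 4-6% |
| 4 co-primary tests, 35% rate | 1% | 3-4% | 4-6% | 6-8% |

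A second simulation (AR(1) correlation 0.8, 3,000 runs) gave 2/12/24/33% and 8/20/28/39% for the 36 tests. Counting 38 tests adds at most 3 points. At 34 per arm, the four co-primary tests reach about 9%.

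**5. Both co-primaries passing by chance.** Sustained relief is nested in 15-minute relief, and the planning text gives both the same rate. In the limit the two endpoints coincide, and the joint error equals the single-test size. At 20 per arm, enumeration gives 2.3% (20% rate) or 2.5% (35% rate) for 3.8 mg, and 4.2% or 4.7% for either dose.

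**6. What the intervals would show.** Illustrative tables, active vs placebo:

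| Responders | Fisher p | Conditional OR (exact 95% CI) | Difference, points (Newcombe 95% CI) |
|---|---|---|---|
| 6/10 vs 2/10 | 0.17 | 5.4 (0.6 to 80) | 40 (-2 to 67) |
| 8/15 vs 3/15 | 0.13 | 4.3 (0.7 to 34) | 33 (-1 to 59) |
| 11/20 vs 4/20 | 0.048 | 4.7 (1.01 to 26.5) | 35 (5 to 58) |

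All come from the same 2×2 tables as the Fisher test. With equal arms of 6, 10, 15 or 20 at 20% vs 55%, the exact odds-ratio CI never disagrees with Fisher at 0.05, while the Newcombe CI disagrees in 22/15/18/12% of trials. With mildly unequal arms (11:9, 9:11, 21:18, active:placebo) the exact CI disagrees in 3/8/6% and Newcombe in 12/9/6%.

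**The case against.** **The sequence was tied to CMH.** Protocol 7.4.2 orders the protocol's own analyses, and once CMH goes, the sequence as described has lost its component tests. That is a fair account of SAP 12's second reason. It explains why the tests change, but not why the order must go.

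**The odds ratios went with the CMH analysis.** Protocol 7.4.1 promises them in the same paragraph, so withdrawing that analysis arguably withdraws them. What stands is that SAP 12 does not name the loss and that unstratified estimates remain computable.

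**Nothing is hidden.** A reader might infer that the loss of multiplicity control is concealed. It is not: SAP 7.1.1 and 12 state it openly, the SAP keeps co-primary and secondary endpoints apart, and section 7.2 describes the latter as tested to understand benefit better.

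**Replacing CMH.** A reader might infer that the switch to Fisher's test is itself an error. The documents do not show that. Without counts by arm and subtype the reason cannot be checked, but an unstratified exact test is reasonable when numbers are very small.

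**Size.** Treating the 36 tests as independent at a full 5% gives 1 − 0.95³⁶ = 84%. That overstates the risk, because the tests are correlated and Fisher's test is conservative. At about 10 per arm or fewer, power for the first gate is 19% or less, so the sequence and a plain nominal label would give nearly the same report. This objection stands.

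**Conclusion.** The point holds and should be fixed. Neither reason in SAP 12 requires abandoning the order, and the promised odds ratios with CIs drop out of SAP 9.1 and 9.2 unnamed. These are facts of the text. The size of the harm is less certain, because the documents give neither the actual N nor the correlations between endpoints. On the assumed 6 to 20 per arm, the exposure lies mainly in the secondaries, which SAP 9.2 reports without an order or a nominal label.

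The co-primary conclusions are not seriously inflated. Requiring both endpoints keeps the chance error below 5% at 20 per arm, even for either dose. But the SAP does not itself say that both must be met for a dose.

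**What to change.** 1. **SAP 7.1.1, before unblinding:** apply the protocol sequence to the Fisher p-values. Test both co-primaries for 3.8 mg, then both for 1.9 mg, then a listed order of secondaries. State that both co-primaries must be met for a dose, and label every result after the first non-significant one as nominal. Say whether rescue use is tested. If treatment codes are already known, do not set an order. Instead label all p-values outside the 3.8 mg co-primary pair as nominal.
2. **SAP 9.1 and 9.2:** report for each dose versus placebo the odds ratio with an exact conditional 95% CI. A risk difference with CI may be added as descriptive.
3. **SAP 12:** remove low enrolment as the reason for dropping the order, and name the change to the odds ratios and CIs. Counts by arm and subtype would be helpful but are optional.

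**Cost.** SAP wording and a few lines of code. Fewer results can be called significant, and the intervals will be wide. Protocol 7 requires the SAP to be final before database lock and unblinding, but the documents do not show whether the codes were still concealed. Anything added afterwards should be identified in the CSR as SAP 4.2 provides.

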#### 13. APPENDICES

## 13.1 Appendix 1

The following reporting conventions will be adopted for the presentation of study data. These conventions will enhance the review process and help to standardize presentation with common notations

## 13.1.1 General Reporting Conventions

- All tables and data listings will be developed in Landscape Orientation, unless presented as part of the text in a clinical study report (CSR).
- Specialized text styles, such as bolding, italics, borders, shading, superscripted and subscripted text will not be used in tables, figures, and data listings unless they add significant value to the table, figure, or data listing.
- Only standard keyboard characters should be used in tables and data listings.
   Special characters, such as non-printable control characters, printer specific, or font specific characters, will not be used on a table, figure, or data listing.
   Hexadecimal character representations are allowed (e.g., μ, α, β).
- All titles will be centered on a page. The ICH numbering convention is to be used for all tables, listings, and graphs (TLGs).
- All footnotes will be left justified at the bottom of a page. Footnotes must be present on the page where they are first referenced. Footnotes should be used sparingly and must add value to the TLG. If more than four footnote lines are planned then a cover page may be used to display footnotes.
- Missing values for both numeric and character variables will be presented as blanks in a table or data listing. A zero (0) may be used if appropriate to identify when the frequency of a variable is not observed.
- All date values will be presented as DDMMMYYYY (e.g., 29AUG2001) format. A four-digit year is preferred for all dates.
- All observed time values will be presented using a 24-hour clock HH:MM:SS format (e.g., 01:35:45 or 11:26). Seconds should only be reported if they were measured as part of the study.
- Time durations will be reported in mixed HHhr MMm SSs notation (e.g., 5h 32m, or 27h 52m 31s). The use of decimal notation to present (display) time durations should be avoided (e.g. 0.083h = 5m) unless it is necessary to show

Protocol: CP-2019-001 Page 26 of 26

Final Version 1.0

the computation of time differences in a table, figure, or data listing, in which case both notations may be used to display the time duration.

- All TLGs will have the name of the program, location, and a date stamp on the bottom of each output.
- All analysis programs developed for a TLG display will be self-contained to facilitate transfer of programs to multiple computing environments and transfer to a regulatory agency (if requested).

## 13.1.2 Population Summary Conventions

- Population(s) represented on the tables or data listings will be clearly identified in the last title of the Table as "<name of population>" and will be identical in name to that identified in the protocol or SAP.
- Consistent terminology will be used to define and identify a population. Common nomenclature may include (a) All Subjects, (b) ITT, (c) Safety, and (d) PP.
- Sub-population(s) or special population(s) descriptions will provide sufficient detail to ensure comprehension of the population (e.g., ITT >60 years of age) used for analysis in a table or figure.
- Population sizes may be presented for each treatment or dosing category as totals in the column header as (N=xxxx), where appropriate.
- Population sizes shown with summary statistics are the samples sizes (n) of Subjects with non-missing values.
- All population summaries for categorical variables will include all categories that were planned and for which the subjects may have had a response. Percentages corresponding to null categories (cells) will be suppressed.
- All population summaries for continuous variables will include: n, mean, SD, minimum, and maximum. Other summaries (e.g. number missing, median, quartiles, 95% confidence intervals, CV or %CV) may be used as appropriate.
- All percentages are rounded and reported to a single decimal point (xx.x%).
   A percentage of 100% will be reported as 100%. A percentage of zero will be reported as 0.
- Population summaries that include *P* values will report the *P* value to three decimal places with a leading zero (0.001). All *P* values reported on default output from statistical software (i.e., SAS® Software) may be reported at the default level of precision. *P* values <0.001 should be reported as <0.001 not 0.000.
